#### **Protection of Data Security and Confidentiality:**

**Blinding to reduce bias.** All patient-derived samples will be stored and analyzed using only a random Subject ID number, and all research will be kept blinded as to patient disease state, and all analyses of mechanistic data (flow cytometric measurements, qPCR measurements, Western Blots etc.) will be completed prior to unblinding of research investigators.

**Data security.** All subjects will be assigned a unique numerical identifier, and study data will be stored in a password-secured electronic database on a dedicated server. Double-keyed entry will be used to enter the data to ensure the highest levels of validity. The two generated files are compared using a verification program that checks any discrepancies among double-keyed entry. Before being added to the database, the data undergo further within-form and across-time verifications to assure completeness, accuracy, and participant identification number. Any errors in coding or keying are corrected promptly. Questionable data that need additional review are sent to a separate file and then resubmitted to the validation program after problem resolution. Nightly backups of all data files are made. All database files can be imported in SAS software for validation and data analysis.

**Data confidentiality.** All data will remain confidential within the investigation site. A record of study subjects entered will remain strictly confidential and will be coded only by a study identification number assigned to each subject at the time of enrollment. While the study is in progress, identifying information will be maintained to enable collection of all follow-up data.

All subject CRFs will be coded with a unique patient identifier, which will identify that subject only at the investigational site staff level. All direct subject contact (informed consent, subject screening and study procedures) and relevant confidentiality protections will be the responsibility of the PI. There should be no risk to subject confidentiality because all records associated with this study will be confidential within the study staff environment within the AERD Center. Safety precautions, password protection and encryption of data, will ensure that electronic systems will not be a risk to subject confidentiality.

**Confidentiality of genetic data information.** Tissue samples will be taken, from which cell populations will be isolated for genetics studies. The relevant tissue specimens and isolated cell populations for the genetics studies will be labeled with a unique numerical identification code. Subject name or other identifiers will not be placed on the genetics specimens. The key to the code will connect the subject's name to the subject's study information and specimens. The key to the code will be kept in a separate electronic database file and subject's genetic specimens will always remain coded and their identity will remain confidential.

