**Overview.** To exert effects, IL-5 induces phosphorylation and activation of several JAK and STAT proteins, and may be involved in regulation of transcripts involved in B-cell maturation, differentiation, and survival. While IL-5 supports murine plasma cell survival, IL-5-driven survival of human plasma cells has not been demonstrated. Our preliminary data has confirmed that IL-5R $\alpha^+$  plasma cells are enriched in nasal polyps, suggesting a disease-specific mechanism that may sustain antibody production. Moreover, our studies suggest that IL-5 can upregulate expression of transcripts involved in proliferation, survival, migration and class switch in these cells. In this Sub-Aim, we will test the **hypothesis that IL-5 stimulation of nasal polyp plasma cells induces signaling (A) and regulates transcriptional activity relevant to pathogenetic function (B)**.

**Methods.** **(A)** To determine the signaling capability of IL-5R $\alpha$  on nasal polyp plasma cells, we will measure the phosphorylation status of their JAK1/JAK2 and STAT1/STAT5, which are rapidly activated upon IL-5 binding to IL-5R $\alpha$  and can be surrogates of IL-5R $\alpha$  signaling *in vivo*. We will prospectively collect surgical samples and digest nasal polyp tissue from 5 AERD patients and 5 CRSwNP patients into a single cell suspension as above, and sort plasma cells as CD38 $^{HI}$ /CD27 $^{HI}$ /CD138 $^+$ /CD20 $^-$ . These will be evaluated using intracellular flow cytometry for phosphorylated JAK1, JAK2, STAT1, and STAT5. We will first measure the phosphorylation levels on freshly isolated cells, to determine differences in their baseline *in vivo* status. We will also measure their phosphorylation levels following a 6h and 24h stimulation with or without IL-5 (1, 10 and 100 ng/mL), as described previously, to confirm their IL-5R $\alpha$  signaling capacity. We will use BD Phosflow™ to optimize fixation and permeabilization for flow cytometric analysis of intracellular phosphoproteins. **(B)** To verify the transcriptional consequence of IL-5 signaling on plasma cells, we have already collected and sorted nasal polyp plasma cells from 5 patients with AERD and 5 CRSwNP and stimulated them for 6h with or without IL-5 (1, 10 and 100 ng/mL). The stimulated/unstimulated pairs of plasma cells have been collected in TCL buffer,

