and banked for low-input RNA sequencing as above. Going forward, we will conduct differential expression analysis on IL-5-stimulated and unstimulated plasma cells using sample pairing, with a linear model framework. Our criterion for transcripts induced or repressed by IL-5 is that genes are more than twofold changed and obtain a false discovery rate of <1%.

**Anticipated Results.** **(A)** Plasma cell populations with higher IL-5R $\alpha$  expression should exhibit increased phosphorylation of JAK1, JAK2, STAT1, and STAT5 and should demonstrate further increases upon stimulation with IL-5. **(B)** We expect to confirm that IL-5 stimulation of nasal polyp plasma cells induces expression of *CCND2*, *JAK1*, *IKZF1*, *ZBTB44*, *OTG*, *RAP1B*, and *RAC2*, as well as signatures reflecting activation and anti-apoptotic signals (*BCL6*, *AID*, *BLIMP-1*).

**Statistical Analyses.** With a sample size of 6 AERD subjects and 6 CRSwNP subjects, we will be powered at >90%, at a 0.05 level of significance, to detect a difference in antibody-secreting cells that express IL-5R $\alpha$ + between subjects with AERD and CRSwNP. The data will be analyzed as described in Aim 2.

**Pitfalls and Alternative Approaches.** Although the proposed work is largely hypothesis based and furthers recent preliminary observations made by our group, low-input RNA sequencing allows for unbiased analyses. Thus, while we focus on the role of IL-5R $\alpha$ + plasma cells in CRSwNP and AERD pathogenesis, our approach also allows us to identify a range of differentially expressed genes and to broadly phenotype nasal polyp plasma cells.

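### The blinding rule covers disease state only and cannot protect the within-donor IL-5 v no-IL-5 phospho-flow contrasts in Sub-Aim 1b(A)

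*Combined protocol and SAP*

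**What the plan says.** The section on protection of data security and confidentiality, under its paragraph on blinding, states that "All patient-derived samples will be stored and analyzed using only a random Subject ID number" and that "all research will be kept blinded as to patient disease state". It requires analysis of the mechanistic data ("flow cytometric measurements, qPCR measurements, Western Blots etc.) will be completed prior to unblinding of research investigators"). Disease state is the only thing named as masked. No section gives the stimulation condition a code, masks IL-5 concentration, or says how flow gates are set.

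Sub-Aim 1b, Methods (A), takes polyp tissue from 5 AERD and 5 CRSwNP donors, sorts the plasma cells and evaluates them "using intracellular flow cytometry for phosphorylated JAK1, JAK2, STAT1, and STAT5". There are two stages. The first is a baseline comparison: "We will first measure the phosphorylation levels on freshly isolated cells". The second is a stimulation experiment: "We will also measure their phosphorylation levels following a 6h and 24h stimulation with or without IL-5 (1, 10 and 100 ng/mL").

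The Anticipated Results (A) for this sub-aim give the expected direction: populations with higher receptor expression "should demonstrate further increases upon stimulation with IL-5".

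**The concern.** The plan accepts that flow cytometry and blots need blinding, since it lists both under the rule. But the blind is matched to one type of comparison only. It protects the baseline comparison of AERD with CRSwNP. It does nothing for a comparison of two tubes from the same donor, one with IL-5 and one without.

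As written, the plan allows the person reading phospho-flow to know which tube received IL-5, and that person also knows which result is expected. If a positivity gate is placed by eye with that knowledge, a small shift in the expected direction could recur in every donor. Pairing removes differences between donors, but not an error that has the same sign in each pair. At stake is the direct test in Sub-Aim 1b(A) that the receptor signals in human polyp plasma cells.

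**Working it through.** **1. Which contrasts the blind reaches.** Inputs are from Sub-Aim 1b, Methods (A).

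- IL-5 v none: 4 phosphoproteins × 2 times × 3 concentrations = 24 contrasts, all within donor and none protected.
- Disease state at baseline: 4 phosphoproteins = 4 contrasts, all between donors and all protected.

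**2. Why the subject code does not close the gap.** With 3 concentrations plus none at 2 times, one donor yields 4 × 2 = 8 stimulation tubes. A subject number is the same on all eight, so a second label is needed. The plan does not say that this label hides the condition.

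**3. The plan's own figure.** The only stated power (over 90% with 6 AERD and 6 CRSwNP subjects at the 0.05 level) concerns a disease-state contrast in receptor-positive cells. It cannot be reproduced, because no difference or SD is given, and this point does not depend on it.

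**4. Illustration of what a repeated gate shift would do.** The donor numbers (10 pooled, or 5 in one disease group) are from the plan. Everything else is assumed: a Gaussian signal, a percent-positive readout, 10% of unstimulated cells positive, 1000 cells per tube, no true IL-5 effect, extra within-pair SD of 2 or 4 percentage points, and a two-sided 5% paired t-test. The figure of 1000 cells appears in the plan only as RNA-sequencing input in Sub-Aim 1a. No test is named for phospho-flow: the Aim 1 statistics refer to Aim 2, which describes RNA-seq analysis only.

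- Percent positive: P(Z > 1.2816) = 10.0%. With the gate lowered by 0.1 SD in stimulated tubes, P(Z > 1.1816) = 11.87%. With 0.05 SD, P(Z > 1.2316) = 10.91%.
- SD of the paired difference = √[p₀(1−p₀)/1000 + p₁(1−p₁)/1000 + extra²]. For 0.1 SD and 2 points: √(1.395² + 2²) = 2.44 points.
- Noncentrality = (p₁ − p₀)/SD × √n. For 0.1 SD, 2 points and n = 10: 1.87/2.44 × √10 = 2.42. The critical value is 2.262 on 9 df, and the rejection probability is 58%. For n = 5 the critical value is 2.776 on 4 df.

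| Gate shift | Extra SD | False-positive rate, n = 10 | n = 5 |
|---|---|---|---|
| none | either | 5% | 5% |
| 0.05 SD | 4 points | 9% | 7% |
| 0.05 SD | 2 points | 19% | 10% |
| 0.1 SD | 4 points | 24% | 12% |
| 0.1 SD | 2 points | 58% | 26% |

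**5. Check with a simpler bias model.** Suppose the reading bias is 0.25, 0.5 or 1 SD of the paired difference, with no assumption about gates. The same test then rejects in 11%, 29% and 80% of cases with 10 pairs, and in 7%, 14% and 40% with 5 pairs. The pattern is the same.

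**The case against.** The other side has several good arguments, and most of them stand.

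- **Operator-set gates are inferred.** The plan speaks of phosphorylation levels and not of percent positive. Plasma cells are sorted before stimulation, so knowledge of the IL-5 condition cannot move the population gate. An intensity summary of sorted cells would need no positivity cut. This stands: the plan permits condition-aware gating but does not prescribe it.
- **The size rests on assumptions.** No document gives a shift, a baseline percentage or an assay SD. The 58% combines the larger shift, the smaller noise and pooling of both disease groups. This stands, so the full range should be read and not its top.
- **Most IL-5 contrasts are little exposed.** A reader might infer that the study's IL-5 results are at risk as a whole. Aim 2 alone has 10 qPCR markers × (3 acute doses + 1 chronic condition) = 40 contrasts, counting one acute time point, and RNA-seq comparisons come on top. Neither assay involves a gate. The point is confined to phospho-flow.
- **The blot is a different case.** A reader might infer that Western blots are read at 0, 1, 10 or 100 ng/mL with higher values expected. The documents do not support this. Those concentrations belong to the plasma-cell work, which has no blot. The only blot is IL-5Rα in the Aim 2 epithelial cultures. The expectation stated for it is diseased above healthy, which the existing blind covers, and no direction under IL-5 is given.
- **A dose-ordered artefact does not follow.** A single shift between stimulated and unstimulated tubes raises all three concentrations equally. A gradient would need misgating that grows with concentration, and nothing in the plan indicates that.
- **The consequence is limited.** This is an exploratory laboratory study, IL-5 responsiveness is also examined by RNA-seq in Sub-Aim 1b(B), and the one powered comparison is unaffected. This stands, but signalling is a separate stated hypothesis and phospho-flow is its direct test.

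These arguments narrow the point. They do not answer the mismatch between what is blinded and what is compared within donor.

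**Conclusion.** The point holds for the stimulated phospho-flow readings in Sub-Aim 1b(A): 24 within-donor contrasts with a stated expected direction, none protected by the blind on disease state. That conclusion rests on the text alone.

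Whether bias would occur is not shown. On the assumptions listed, a repeated shift of 0.05 to 0.1 SD would lift a nominal 5% error to about 9% to 58% with 10 donors, or 7% to 26% with 5. These figures show how sensitive a small paired comparison is to a consistent reading error. They are not an estimate of the error rate in this study.

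The documents do not support extending the point to a false dose-response, to blots read with a stated IL-5 expectation, or to the qPCR and RNA-seq results. It is a low-cost improvement, worth making before these prospectively collected samples are read.

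**What to change.** Add to the blinding paragraph, in words such as these:

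> Stimulated and unstimulated tubes from each donor will carry a code that does not reveal IL-5 concentration. Any phospho-flow gate will be set once per donor on staining controls, or on one designated control aliquot that is not among the coded tubes, and applied unchanged to all coded tubes. Alternatively, a prespecified intensity summary that needs no cut will be used. The IL-5 code will be opened only after the readouts are locked.

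The control used for gating must lie outside the coded set. If gates were set on the coded unstimulated tube, the reader would have to know which tube that is, and the masking would fail. The plan should also say which of the two readouts, percent positive or intensity, will be analysed.

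The same coding can be applied to the lanes of the Aim 2 IL-5Rα blot as good practice.

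The cost is relabelling, a coded sample list, and having the code held by someone other than the person who gates. The documents do not say who does each task, so whether this needs another member of staff is for the sponsor to check. No extra donors or change in sample size is needed. At most, one control aliquot per donor is set aside if staining controls are not used for gating.
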